6.6 FIGURE 1: Esophageal Transcriptome Analysis

[figure not shown]

Figure 1. Esophageal Transcriptome Analysis: Total RNA from separately acquired biopsy specimens was subjected to EDP signature analysis. (A) The heat diagram depicts the changes after FP exposure in the bidirectional gene dysregulation in each group with reference historical EoE and normal (NL) cohorts ($n = 15$ and 14 , respectively), and the samples at screening (no FP exposure) on the *left*. At the end of phases 1 and 2, expression signatures from FP non-responders (NRs), FP responders with partial remission (PRs), and FP responders with complete remission (CRs) are shown in the heat diagram (yellow, increased expression; blue, decreased expression). (B) On the basis of the expression levels of the 77 diagnostic genes and a dimensionality reduction algorithm, an EoE score reflecting the EoE disease activity was calculated at the end of phase 1 ($**P < .001$, $***P < .0001$, 2-tailed Student t-test). (C) To assess the prediction value of the EDP on FP responsiveness, samples at screening (i.e., pre-FP exposure) and the placebo samples at the end of phase 1 (i.e., pre-FP exposure) were screened by bioinformatics in the context of their subsequent FP responsiveness on the basis of the CR criteria of fewer than 2 eosinophils/HPF in the distal esophagus, where the biopsy specimens were acquired. The 15-gene cluster listed shows a potential for FP efficacy prediction with a P value of less than .05 and fold change greater than 2.0.

6.7 End Of Therapy (EOT) And Follow-Up

The primary efficacy endpoint (e.g. PEES v2 scoring) will be determined at the end of Phase I & II (weeks 12 & 25) at which time all participants will undergo EGD with biopsy. Histologic scoring of biopsy samples obtained during the end of Phase I endoscopy, will be used to determine the treatment pathway to be followed.

Participants who achieve histologic remission at the end of Phase I will have completed the study and will resume follow-up care with their primary GI and/or Allergy physician(s). Those whose disease remains active in terms of histologic disease activity (eosinophil count ≥ 15 per HPF) will go on to Phase II (twelve week treatment with 4FED for Phase I 1FED non-responders **OR** SGC for Phase I 4FED non-responders). This was modified from the original protocol on the basis of discussion with the PAGs, and their strong interest in potentially pursuing a more extensive dietary restriction as a means of achieving symptomatic and histologic improvement in disease activity. The study design is shown schematically in Figure 2 below.

6.8 FIGURE 2: STUDY DESIGN FLOWCHART

[figure not shown]

Figure 2. Study Design Flowchart: Diagram demonstrating the flow of subjects through the study. Following completion of the screening process and EGD #1, subjects undergo randomization into one of the two dietary arms of Phase I. Those subjects who respond histologically following either of the initial dietary therapies will exit the study, and the PEES v2 will be used to score for the presence of symptomatic relief as the primary outcome. Those subjects, who histologically fail dietary therapy, will enter Phase II. Phase I 1FED non-responders will go onto 4FED in Phase II. Phase I 4FED non-responders will be treated with swallowed glucocorticoids. Upon completion of Phase II, EGD #3 would be performed and scoring of symptoms with PEES, and histologic scoring would be performed as seen for those subjects who responded at the end of Phase I.

6.9 Minimization Of Bias And Method Of Treatment Assignment

All eligible participants will be randomized 1:1 to either the 1FED or 4FED. Randomization will be stratified by parameters as determined by our statistician. Following this 3 month phase I, all patients will undergo EGD with biopsy and all those whose disease remains active will move on to Phase II. The sponsor, investigator, select study staff, and participant will all have knowledge of the treatment being received.

6.10 Expected Duration Of Study And Participant Participation

Each participant will participate in the study for a maximum of 36 weeks. This includes a maximum twelve week screening period, followed by 2 sequential 12-week treatment periods. At the end of each 12-week treatment phase there will be a clinic visit and EGD to assess treatment response. Participants whose disease goes into remission will complete the trial at the end of Phase I, and the remainder will move on to the next treatment phase with more extensive dietary restriction or SGC. Participants will have an initial screening visit, followed by clinic visit and EGD at week 12, and (if disease remains active at week 12), a visit to initiate Phase II at around week 13, followed by another clinic visit and EGD 12 weeks later at approximately week 25. It is estimated that the duration of the entire study—including enrollment, performance of study procedures, data collection, analysis, and report writing—will last approximately 2-3 years.

7 STUDY VISITS AND ASSESSMENTS

7.1 TABLE 1. STUDY DESIGN AND SCHEDULE OF ASSESSMENTS

PCORI Diet Study

Phase	Pre-treatment	Treatment Phase 1					Treatment Phase 2			
Visit Number	1	2	3	4	5	6	7	8	9	10
Visit Description	Screening	Enrollment/ Baseline	Phone Visit #1	Phone Visit #2	Phone Visit #3	EOT or Early Withdrawal	Phase 2 Visit 1	Phone Visit #4	Phone Visit #5	EOT or Early Withdrawal
Week	-12 to -1	0	2	4	11	12	13	14	24	25
Perform Informed Consent	X									
Assess Eligibility (inclusion/exclusion criteria)	X	X								
Obtain medical & dietary history	X									
Assess con-meds and/or con-therapies	X									
Vitals (height, weight, BP, heart rate, respiratory rate, temperature)	X	X				X	X			X
Physical Exam	X					X				X
Research Biopsies (taken during SOC EGD)	X ^a					X				X ^b
Study Questionnaires		X				X				X
Dietary Questionnaires		X	X		X		X	X	X	
Skin testing for allergies (prick and patch)		X								
Research Lab Samples	EDP, other ^c	Component Testing				EDP, component testing, other ^c				EDP, other ^c
Morning cortisol (serum)							X			X
CBC with differential	X					X				
Pregnancy test (urine)	X					X				X
Assess AEs			X	X	X	X	X	X	X	X
Assess diet and/or con-med compliance		X	X	X	X	X	X	X	X	X
Provide food diary	X		X		X			X	X	
Provide instructions for diet or medication		X					X			
Determine compliance with treatment			X		X			X	X	X (SGC)
Dispense SGC							X			

^a First SOC EGD used to determine eligibility may be conducted within 12 weeks prior to enrollment visit.

^b This EOT SOC EGD pertains only to Phase 1 Non-Responders.

^c Other refers to collection of blood or saliva for future genetic testing. These samples will only be collected once, but may be collected at any of the visits. Each visit window (for visits 2-10) is ± 7 days.

7.2 Screening (Weeks -12 To -1)

Participants will be screened as above in Table 1. The screening visit should occur at a maximum of twelve weeks prior to the enrollment visit. The research staff member will perform the informed consent process after obtaining informed consent, the following study procedures should be performed and documented up to twelve

weeks prior to the enrollment (Week 0) visit:

- Assess eligibility (inclusion and exclusion criteria)
- Collect medical, surgical and diet history
- Vitals (height, weight, blood pressure, heart rate, respiratory rate, temperature)
- Demographics (age, gender, race)
- Physical exam performed by a study clinician or qualified staff member
- Obtain CBC with differential
- Obtain up to 4 biopsies from the distal and proximal esophagus for research purposes (taken during standard of care EGD)
 - One of these esophageal biopsies will be used for EDP
- Research lab samples (blood or saliva) for future genetic testing may be collected at this visit
- Assessment of concomitant medications and therapies
- Provide food diary
- Pregnancy Test (urine)

Esophageal biopsies for research may be taken during a participant's standard of care EGD (SOC EGD). If the participant has had a SOC EGD and biopsies performed at a participating site or at an outside institution prior to the screening visit (and consent), the results of the EGD may be used to determine eligibility if it falls within the twelve-week window prior to enrollment. In these cases, research biopsies and EREFS evaluation will not be required at baseline. EGDs performed at an outside institution may be used as baseline if the corresponding pathology report and slides are available and the eosinophil counts meet the inclusion criterion of ≥ 15 eosinophils/hpf. In cases where the local pathologist has concerns regarding the eosinophil count, slides may be sent to the CRPC for rapid review in order to verify eligibility. These participants will have all other screening procedures completed at the in-office, screening visit.

CBC results will be obtained from a participant's standard of care lab. The amount of blood drawn (clinical plus research) will adhere to institutional policy limits.

7.3 Phase I: Enrollment & Dietary Treatment (Week 0)

All eligible participants will be enrolled into the study at Week 0 if they meet all entry criteria and have

completed the screening procedures. If a participant is screened and enrolled within a 5 day time frame study procedures that are repeated will only be performed once. At this visit, staff members will:

- Assess eligibility (inclusion and exclusion criteria)
- Measure vitals (blood pressure, heart rate, respiratory rate, temperature), height and weight
- Administer patient and parent-reported outcome questionnaires, which will include a dietary questionnaire to measure intake of the food allergens
- Review food diary (from screening) with subject
- Assess concomitant medications and/or therapies
- Serum collection for component-resolved diagnostics (CRD) [serum IgE component testing], IgG4
- Skin testing for allergies including prick (milk, egg, wheat and soy) and patch testing (milk only).
- Randomize patients to the 1FED or 4FED diet
- Provide standardized dietary instructions for 1FED or 4FED

The participants will be encouraged to call the PI and/or study coordinator if they have any questions, concerns, adverse events, or changes in medication.

7.4 Phone Visits, Phase I

A study staff member will conduct three phone visits (at weeks 2, 4, and 11) during Phase I in order to monitor participants' progress throughout the trial. The following procedures will occur during these phone visits:

- Assess con-med and/or con-therapy compliance
- Assess AEs
- Determine compliance with treatment
 - A dietary questionnaire to measure *intake* of the food allergens will be completed by the participants during weeks 2 and 11 for therapy compliance assessment
 - A food diary will be completed by participants during weeks 2 and 11 to measure adherence

7.5 End Of Treatment Phase I Or Early Withdrawal (Week 12)

For participants who have completed the 12 week Phase I or have withdrawn early from the study, the following procedures will occur:

- Measure vitals (blood pressure, heart rate, respiratory rate, temperature), height and weight

PCORI Diet Study

- Physical exam performed by study clinician or qualified staff member
- Administer patient and parent-reported outcome questionnaires
- Assess AEs
- Obtain up to 4 biopsies from the distal and proximal esophagus for research purposes (taken during standard of care EGD)Research lab samples:
 - Esophageal biopsy for EDP
 - Serum (~2 tsp, or 10 mL) for serum IgE/CRD/IgG4
 - Blood or saliva for future genetic testing may be collected at this visit
- Obtain CBC with differential (SOC)
- Assess participant compliance with diet and concomitant medications
- Pregnancy Test (urine)

If a participant withdraws from the study before completing 12 weeks of dietary therapy, the end of treatment/early withdrawal visit, should be conducted within one week of the participant's stopping dietary therapy. Participants should stay on their dietary therapy until results of biopsies are communicated to them. Those participants who have resolution of their inflammation on endoscopy will complete the study at this time while those with continued active inflammation will move on to the next phase, which consists of either 4FED (for Phase I 1FED non-responders) or swallowed fluticasone therapy at 880 mcg twice a day while back on an unrestricted diet (for Phase I 4FED non-responders).

7.6 Phase II Visit 1 (Week 13)

Those participants who have completed the Phase I diet protocol but have continued active inflammation will return to clinic once their biopsies have been read, within 1 week of their EGD. At this visit, the following procedures will occur:

- Measure vitals (blood pressure, heart rate, respiratory rate, temperature), height and weight
- Assess AEs
- Assess participant compliance with concomitant medications
- Provide standardized instructions for administration of the fluticasone for those moving on to SGC
- Provide standardized instructions for 4FED to participants who will be on 4FED
- Provide diet or medication diary/log to participants

PCORI Diet Study

- Administer dietary questionnaire to all participants to measure *intake* of the food allergens. Review food diary (from Visit #5) for those who will be on 4FED
- Dispense the fluticasone to the participant for those moving on to SGC
- Measure morning cortisol (serum, ~1 tsp or 5 mL) for those moving on to SGC

7.7 Phone Visits, Phase II

A study staff member will conduct two phone visits (at weeks 14 and 24) during Phase II in order to monitor participants' progress throughout the trial. The following procedures will occur during these phone visits:

- Assess con-med and/or con-therapy compliance
- Assess AEs
- Determine compliance with treatment
 - A dietary questionnaire to measure *intake* of the food allergens will be completed by the all participants during week 14 and 24. The questionnaires will be used for therapy compliance assessment for those on 4FED.
 - A food diary will be completed by participants who are on 4FED during weeks 14 and 24 of the trial to measure adherence

7.8 End Of Treatment Phase II Or Early Withdrawal (Week 25)

For those participants who have completed the Phase II therapy or have withdrawn early from the study, the following procedures will occur:

- Measure vitals (blood pressure, heart rate, respiratory rate, temperature), height and weight
- Physical exam performed by a study clinician or qualified staff member
- Administer patient and parent-reported outcome questionnaires
- Assess AEs
- Obtain up to 4 biopsies from the distal and proximal esophagus for research purposes (taken during SOC EGD)
- Assess participant compliance with concomitant medications/therapies
- Assess participant compliance with therapy (SGC)
- Pregnancy Test (urine)
- Measure morning cortisol (serum, ~1 tsp, or 5 mL) for those treated with SGC
- Research lab samples

PCORI Diet Study

- Esophageal biopsy for EDP
- Blood or saliva for future genetic testing may be collected at this visit

If a participant withdraws from the study before completing this 12 weeks of SGC or 4FED therapy, the end of treatment/early withdrawal visit should be conducted within one week of the participant's stopping therapy. Participants should stay on SGC or 4FED until results of biopsies are communicated to them. Following the receipt of their biopsy results, the patients will return to standard clinical care.

7.9 Pregnancy

Should pregnancy occur during either phase of the study, dietary therapy and/or dosing of study medication will be discontinued and the participant will be withdrawn from the study. The pregnancy will be followed clinically to term.

7.10 Unscheduled Visits

Unscheduled visits will take place for any complication or AE/SAE that requires an extra visit. The procedures to be performed at the unscheduled visits will be at the discretion of the PI. Procedures that may be performed at an unscheduled visit include:

- Vital signs (blood pressure, heart rate, respiratory rate, temperature), height and weight
- Physical exam
- Assess AEs
- Lab tests
- Assess/address problems with dietary adherence

These visits will be documented in the unscheduled visit case report.

8 SELECTION AND WITHDRAWAL OF PARTICIPANTS

8.1 Participant Inclusion Criteria

At study enrollment, subjects will be eligible if they:

- Have diagnosis of EoE (based on consensus criteria)³
- Are aged 6 to 17 years
- Have histologically confirmed active disease ≥ 15 eosinophils/hpf in either distal or proximal esophagus within 12 weeks of enrollment visit
- PPI confirmation

- Symptomatic (have experienced symptoms within the last month prior to enrollment)
- Has a negative urine pregnancy test at screening if of childbearing potential. Females of childbearing potential must have a negative urine pregnancy test (β -hCG) prior to enrollment into the study (i.e., at screening). Subsequently, these participants must agree to use adequate birth control measures (e.g., condom, oral/injectable/subcutaneous contraceptives, intrauterine device, or sexual abstinence) during the study and for at least one month after the last dose of study drug which will be documented in the source documents.

8.2 Participant Exclusion Criteria

Subjects will be excluded if they:

- Have been treated with topical swallowed steroids within the last 2 months or systemic steroids within the past 3 months
- Have eosinophilia in segments of the GI tract other than the esophagus
- Have been diagnosed with a GI malabsorption disorder (i.e., Inflammatory bowel disease, Crohn's disease) or Celiac disease
- Are currently on dietary therapy avoiding milk (i.e. on a 1FED), or milk, egg, soy, and wheat (i.e. on a 4FED)
- Have concurrent H pylori gastritis or parasitic infection
- Are unable to obtain EGD with esophageal biopsies at CCHMC or other participating institution within 4 weeks of study completion
- Have previously failed (in a clinical trial setting) dietary therapy with one of these regimens or topical steroid treatment with fluticasone at a total dose of 1760 mcg per day.
- Have definitely responded (in a clinical trial setting) to either dietary therapy avoiding these antigens or to swallowed fluticasone at a total dose of 1760 mcg per day
- Are concurrently receiving any of the prohibited medications listed in Table 2
- On immunotherapy for pollen (if not on maintenance therapy) or IgE-mediated food allergy.
- Not fluent in English

9 PARTICIPANT WITHDRAWAL CRITERIA

An intent to treat approach will be used. All data acquired prior to termination for the reasons outlined below will be included in the primary analysis unless patient withdraws consent. Every effort will be made to conduct

a final study visit with the participant and participants will be followed clinically until, if applicable, all adverse events resolve.

- Withdrawal of consent
- Withdrawal by the participant
- Withdrawal by the investigator
- Intercurrent illness or event that precludes further visits to the study site or ability to evaluate disease (e.g.-mental status change, large pleural effusion).
- Participants will be discontinued from the study if they are unable to comply with the dietary restrictions or develop severe complications from their EoE (e.g., esophageal strictures).

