There will be two sets of analysis populations in terms of efficacy assessment, the intent-to-treat and per protocol. All patients randomized to Phase I of the study who have at least one clinical observation post randomization will be considered in intent-to-treat set. Patients who are at least 80% compliant to dietary assignment during Phase I, and who do not have any major protocol violations will be considered in per protocol set. If there is more than 10% difference in patient numbers between these two populations, the primary efficacy analysis will be performed on both intent-to-treat analysis and per protocol populations. Otherwise, all analyses will be based on intent-to-treat population. Patients who do drop out of the trial before the end of Phase I will have their PEES done at the time of dropout.

The primary endpoint is overall PEES score change from pre-treatment to the end of Phase I. If normality assumption is approximately valid, a linear mixed effect model will be applied to the primary efficacy variable, account for site random effect, and other potentially important covariates, e.g. gender, race, and PPI use etc. Pertaining to the specific aim, the comparison of response (PEES change from baseline) will be made between 1FED and 4FED groups via the above model. Because of non-normal nature of the scores observed in previous research, a Wilcoxon rank sum test may be applied to compare between two treatment groups when normality is violated.

As a secondary endpoint analysis, remission rates (as defined by the percentage of participants achieving histologic remission (eosinophils less than 15/HPF) at the end of Phase I will be compared between the two treatment groups using the generalized linear mixed effects model with the logit link (for binary outcome) that accounts for the clustering within sites. Important covariates will be analyzed in this model including gender, race, PPI use, atopy, age, and anthropomorphic features. Treatment group comparisons for secondary endpoints will be performed using the generalized linear mixed effects model using the link that is appropriate for the endpoint (i.e. logit for binary, log for Poisson count, identity for continuous). These models will account for the

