6 STATISTICAL METHODS

6.1 Statistical Analyses: Aim 1

Demographic and patient characteristics will be summarized for the two treatment groups using mean \pm standard deviation or median [interquartile range] for continuous variables and frequency and percentages for categorical variables. Treatment comparisons will be performed using the two-sample t-test or Wilcoxon Rank sum test for continuous variables and the Fisher's Exact test for categorical variables. All tests will be conducted at $\alpha=0.05$, including the primary and secondary analyses.

There was going to be two sets of analysis populations in terms of efficacy assessment, the intent-to-treat and per protocol. However, since the total enrollment has been reduced to about 50, all patients randomized to Phase I of the study who have at least one clinical observation post randomization will be considered in intent-to-treat set. Only this set of population will be included in the statistical analyses. Originally, we plan to define patients who are at least 80% compliant to dietary assignment during Phase I, and who do not have any major protocol violations as in per protocol set. Now all analyses will be based on intent-to-treat population. Patients who do drop out of the trial before the end of Phase I will have their PEES done at the time of dropout. The primary endpoint is overall PEES score change from pre-treatment to the end of Phase I. If normality assumption is approximately valid, a linear mixed effect model will be applied to the primary efficacy variable,

account for site random effect, and other potentially important covariates, e.g. gender, race, and PPI use etc. Because of non-normal nature of the scores in previous research, a Wilcoxon rank sum test may be applied to compare between two treatment groups when normality is violated.

As a secondary endpoint analysis, remission rates (as defined by the percentage of participants achieving histologic remission (eosinophils less than 15/HPF) at the end of Phase I will be analyzed in the following 3 steps.

- (1) Remission rates will be computed along with their 95% CIs for each diet group separately;

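### Children who cannot keep the diet leave the study and are scored at dropout, so a Week-12 comparison labelled intent to treat can mix assessment times, with no rule for the early scores

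*Protocol*

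**What the plan says.** Protocol Section 9 begins "An intent to treat approach will be used" and continues "All data acquired prior to termination for the reasons outlined below will be included in the primary analysis unless patient withdraws consent". The reasons it then lists include this one: "Participants will be discontinued from the study if they are unable to comply with the dietary restrictions".

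Protocol Section 7.5 uses one visit for both Week 12 and early withdrawal. For a child who stops early, that visit "should be conducted within one week of the participant's stopping dietary therapy". Protocol Section 12.2 and SAP Section 6.1 carry the same scoring rule: "Patients who do drop out of the trial before the end of Phase I will have their PEES done at the time of dropout". SAP Section 6.1 then defines the target: "The primary endpoint is overall PEES score change from pre-treatment to the end of Phase I".

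Other provisions that bear on the point:

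- SAP Section 6.1 drops the per-protocol set. It analyses only the intent-to-treat set, meaning randomized children with any clinical observation after randomization.
- SAP Section 6.2 expects a questionnaire from early dropouts too, leaves a missing total score unimputed, records reasons for dropout and compares dropout rates between arms.
- Protocol Section 9.1 replaces children who do not reach Week 12 and its EGD, but keeps every enrolled child in any intent-to-treat analysis.

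**The concern.** An intent-to-treat comparison at Week 12 needs a Week-12 outcome from every randomized child who still consents, whatever that child is eating. Section 9 makes failing the assigned diet a reason to leave the study, so the last PEESS for such a child is taken when the diet stops, which may be well before Week 12. Stopping the diet and leaving the study are treated as one event.

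Dropout unrelated to treatment would mainly add noise. This dropout can be caused by the treatment, because the two arms differ in how much food they remove. If children stop at different rates or times in the two arms, one arm holds more early scores than the other, and part of the observed PEESS difference reflects timing. Replacing those children adds new scores but does not recover the missing Week-12 outcomes. With the per-protocol set gone, no second analysis would show whether the result depends on the early scores.

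**Working it through.** **1. When each child's Phase I score is taken**

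| Child | Phase I PEESS | Source |
|---|---|---|
| Completes Phase I | Week 12, ±7 days | Protocol Table 1 |
| Stops early, attends the final visit | Within a week of stopping, at any point in Phase I | Protocol 7.5, 12.2; SAP 6.1 |
| Stops early, no final questionnaire | None, not imputed | SAP 6.2 |

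I found no provision for a Week-12 PEESS in the second row, no adjustment for time of assessment and no sensitivity analysis. The follow-up that Section 9 keeps is clinical, until adverse events resolve.

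**2. Whether the use of the early score is stated**

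No sentence says that the dropout score takes the place of the Week-12 score. It follows from Section 9 (data before termination go into the primary analysis), Section 12.2 and SAP 6.1 (PEESS at dropout), and SAP 6.2 (a questionnaire expected despite early termination). The sample size treats the same children differently. Reproducing it with the Noether formula for the Wilcoxon test, two-sided 0.05, 80% power:

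- P(4FED change exceeds 1FED change) = 0.5 × 0.80 + 1.0 × 0.20 = 0.60
- Total N = (1.960 + 0.8416)² / [12 × 0.5 × 0.5 × (0.60 − 0.50)²] = 7.849 / 0.03 = 261.6, so 131 per group
- 131 / 0.90 = 145.6, so 146 per group and 292 in total

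The plan's figures reproduce and are not in error. But the 10% inflation counts dropouts as contributing nothing, while Sections 9 and 12.2 keep their scores. The handling rule therefore needs to be written down.

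**3. How many scores are exposed**

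At the stated 10% rate: 0.10 × 292 = 29.2, about 29 children. At the revised enrolment of about 50 (SAP 4.1): 0.10 × 50 = 5.

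**4. Direction and size**

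Let p be the share of an arm with an early score, and d the mean gap in those children between the dropout-time change and the change at Week 12. The shift in the arm difference is p₄d₄ − p₁d₁ (4FED minus 1FED). The documents give none of these four quantities.

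The sign can be explored with the protocol's own construction, P = 0.5 + (r₄ − r₁)/2. Assume an early score shows a fraction f of the response that would have been seen at Week 12, so r = planned rate × [1 − p(1 − f)], with planned rates 45% and 65%. The splits below average the stated 10%; the splits and f are assumptions.

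| Early scores, 1FED / 4FED | P at f = 0 | P at f = 0.5 |
|---|---|---|
| 10% / 10% | 0.590 | 0.595 |
| 5% / 15% | 0.5625 | 0.581 |
| 15% / 5% | 0.6175 | 0.609 |

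For example, 5% / 15% at f = 0: r₁ = 0.45 × 0.95 = 0.4275; r₄ = 0.65 × 0.85 = 0.5525; P = 0.5 + 0.125/2 = 0.5625. At f = 1 every row returns 0.60. The shift runs from −0.0375 to +0.0175 and changes sign with the split. This shows only that the direction is open.

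**The case against.** The best defence has four parts.

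- **The removed group may be small.** Section 9 speaks of inability to comply, not of any lapse. The protocol's planned per-protocol set, at 80% compliance, makes sense only if less compliant children stay in, and Section 7.10 allows visits to work on adherence. This stands. It limits how many children are affected, but does not supply a rule for those who are.
- **A score near stopping can answer a legitimate question,** namely symptoms while on the assigned diet. That is true, but the plan does not claim it. It states intent to treat and an end-of-Phase-I endpoint.
- **The illustration in the working is not an estimate of bias.** A child off the diet at Week 12 might be a non-responder then too, in which case an early score showing no response would agree with the Week-12 score. This stands, and is why the illustration is used only for direction.
- **There are partial safeguards:** an effort to hold a final visit, and dropout compared by arm. These would detect an imbalance in dropout but not correct for it.

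A reader might go further in three ways that the documents do not support. One is that early stopping will be commoner on 4FED. No dropout or adherence figure by diet is given. Protocol Section 3.2 calls adherence hard on any elimination diet, and Section 4.11 says less restrictive diets may fail more often, which could add withdrawals on 1FED. Another is that the plan prescribes last observation carried forward; that is an inference from several sections. The third is a bias in PEESS points as a share of the planned effect. The sample size rests on response rates, no effect in points is stated, and Section 6.5.1.1 notes that symptoms and histology can dissociate.

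**Conclusion.** The point holds as a conflict between the intent-to-treat label and the data the plan will collect, together with an unstated rule for early scores. Followed as written, the plan lets dropout-time and Week-12 scores enter the same primary comparison, in proportions that may depend on the assigned diet. The bias has unknown direction, and its size cannot be stated from the documents. Exposure at the plan's 10% rate is about 29 of 292 scores, or about 5 of 50. The conclusion rests on reading Protocol Sections 7.5, 9 and 12.2 with SAP Sections 6.1 and 6.2, and on stopping being able to follow from the diet. It does not rest on which arm stops more. The change is worth making because it is cheap and brings the data into line with the plan's own label.

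**What to change.** **Protocol.** Reconcile the study-discontinuation wording in Section 9 with the intent-to-treat statement by separating stopping the diet from leaving the study. Unless consent is withdrawn, collect the parent-report PEESS at Week 12 by mail or phone and use it in the primary analysis. Keep the dropout-time PEESS as an additional record. No clinical or diet rule is proposed.

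**SAP, before the database is final.** SAP Section 4.1 already records curtailed enrolment, so Week-12 collection can help only children who have not yet passed Week 12. For those who have left, state how dropout-time scores are used, report their number and timing by arm, and add a sensitivity analysis of the primary comparison with and without them.

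**Cost.** One extra questionnaire contact for the few who stop early. The questionnaires are paper forms (Protocol Section 13.3) and the study already makes phone contacts (Section 7.4); no extra visit or EGD is needed. The downside is that some Week-12 scores will reflect time off the diet, which a comparison by assigned diet accepts.
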